**Table 1 Overview of Planned Study Population Analyses**

Display Type	Data Displays to be Generated		
	Table	Figure	Listing
Subjects Disposition			
Subject Population Disposition	Y		
Subject Study Status & Withdrawal Reason	Y		
Inclusion/Exclusion Criteria	Y		
Enrollment	Y		
Subjects Demographic and Baseline Characteristics			
Demographic Characteristics	Y		Y
History of Tobacco Use and Alcohol Use	Y		
Pregnancy**	Y		
SLEDAI 2000	Y		
Disease Condition			
Medical History	Y		
SLE Diagnosis Duration	Y		
Laboratory Tests			
Laboratory Test Parameters*	Y		
Treatment Switching relative to Initial Cohort			
Exposure switching (BENLYSTA start/stop)	Y		Y
Reasons for switching (starting or stopping Benlysta)	Y		Y
Withdrawal and Reason for Withdrawal			
Withdrawal from study	Y		
Reason for withdrawal	Y		Y

NOTES: Y = Yes; implies display type (Table, Figure, Listing) generated. Empty cells implies 'No' display type generated. \* See list of tests in Appendix 7 (Section 9.7); \*\* female participants only

The following statistical analyses to describe the rate and risk/probability of study withdrawal will be performed:

- Study Withdrawal rate (see details of methodology in Section 7.1.5)
- The rate of Study Withdrawal using Kaplan–Meier (KM) estimator (see details of methodology in Section 7.1.5)
- Survival Probability (the probability of not withdrawing from the study)

## 7. STATISTICAL ANALYSES

The data displays of the final analysis are shown in Appendix 11. Unless otherwise specified, analyses will be performed using ‘Evaluable’ analysis population, and presented separately for ‘Current Users’ and ‘Treatment Initiators’ study cohorts.

### 7.1. Safety Analyses

For all primary endpoint analyses (AESIs) comparison is by exposure group (BENLYSTA and NON-BENLYSTA) defined based on exposure assignment strategies described in Appendix 2 (Section 9.2): ‘Initial Exposure’, ‘As-Exposed’ (Time Varying), and/or ‘Ever-Exposed’. The exposure strategy used for each endpoint will be indicated on the data displays list (Appendix 11) and on the actual Tables, Listings and Figures (TLFs).

An overview of planned safety analyses is presented in Table 2. Details of the data displays for the planned analyses are presented in Appendix 11: List of TLF Data Displays (Section 9.11.2).

**Table 2 Overview of Planned Safety Analyses**

Endpoint	Absolute						Change from Baseline			
	Stats Analysis		Summary		Individual		Summary		Individual	
	T	F	T	F	F	L	T	F	F	L
Adverse Events of Special Interest (AESI)										
Overall and specific AESIs experienced during follow-up (section 2.2)	Y		Y			Y 				

Listing will include individual's subject study ID, adverse event's (AE's) & AE system organ classes, preferred terms and verbatim text.

NOTES:

- T = Table, L = Listing, F = Figure, Y = Yes display type generated. Empty cells implies ‘No’ display type generated.
- Stats Analysis = display type for statistical analysis (i.e. modelling and computation of rates) of event count data.
- Summary = display type for any summaries (i.e. descriptive statistics) of the observed raw data.
- Individual = display of individual subject observed raw data.

#### 7.1.1. Endpoint / Variables

The primary safety endpoint is each category of AESI (listed in Section 2.2) experienced by subjects during study follow-up period.

### **7.1.2. Summary Measure**

The summary measures for the safety endpoints specified in Table 2 are:

AESI endpoints

- Cumulative count of all AESI combined and count of subjects (number and percentage) experiencing at least one AESI.
- Cumulative count of each specific AESI category and count of subjects (number and percentage) experiencing at least one occurrence of each specific AESI category.
- Incidence proportion (expressed as a %) for each specific AESI category.
- Incidence rate (Section 7.1.5.1) for each specific AESI category.
- Event rate (Section 7.1.5.1) for each specific AESI category (except mortality).

### **7.1.3. Population of Interest**

The primary safety analyses will be based on the “Evaluable” analysis population, unless otherwise specified.

### **7.1.4. Strategy for Intercurrent (Post-Randomization) Events**

Not applicable.

### **7.1.5. Statistical Analyses / Methods**

Unless otherwise specified, endpoints/variables displayed in Section 7.1.1 will be summarised as specified in Section 7.1.2. Details of the planned displays for each endpoint are provided in Appendix 11: List of TLF Data Displays.

The statistical analysis method for estimation of rate and 95% CI are described below.

### 7.1.5.1. Statistical Methodology Specification Related to AESI Endpoints

Endpoint / Variables

Incidence and event rates will be calculated for the following endpoints/variables (unless otherwise specified):
 
 
• Each category of AESI experienced by subjects as listed in Section 2.2
 

Endpoint Specification

1. Incidence rate will be calculated for each exposure group as follows:
 $\text{Incidence Rate} = \frac{\sum \text{at risk subjects with at least one event}}{\sum \text{subject years at risk}} \times 100$ 
 
- Incidence rate is defined as the number of 'at-risk' subjects experiencing first event (i.e. number of new cases) during the specified follow-up period divided by total subject-years at-risk of that event for all subjects at risk.
 
- Although the categorization of study follow-up time to Benlysta (Exposed) or Non-Benlysta (Unexposed) depends on the exposure assignment strategy (see Appendix 2, Section 9.2.1 for further discussion), the follow-up time included in the subject-years at-risk calculation, for each month xx time period, starts from enrollment date and ends at the earliest of the following: 
 
o First event date
 
o Last contact date (as defined in Section 9.5.3)
 
o Month xx target date (Section 5.3)
 
o Censored date (for While on Initial Exposure strategy; see Section 9.2.1.1)
 
o Data cut-off date
 
 
Additionally, for some exposure strategies (e.g. 'As-Exposed' strategy; see Appendix 2, Section 9.2.1.2), time to treatment switch and risk windows are also considered when categorizing follow-up time into 'Exposed' and 'Unexposed' period.
 
 
- Calculation of an individual's subject-years at-risk for each exposure strategy is shown in Section 9.2.
 
- Subject-years at-risk will be calculated for each event type separately.
 
- Only the first experience of the event (i.e. new cases) or first primary diagnosis (in the case of a malignant event) which occurred during the 'at-risk' period are counted (see Section 9.2.1 for time period considered for each exposure strategy).
 
- For summary of each specific AESI category, subjects experiencing events in multiple AESI categories will be counted in more than 1 AESI category.
 
 
2. Event rate will be computed for each exposure group as follows:
 $\text{Event rate} = \frac{\sum \text{all AESI events}}{\sum \text{subject years of follow-up}} \times 100$ 
 
- Event rate is estimated for potentially recurrent events and represents the average number of events per unit time of follow-up. It is defined as the total number of events experienced by all subjects during the specified study period divided by subject-years of follow-up. The categorization of study follow-up time depends on the exposure strategy (see Appendix 2, Section 9.2.1). The subject-years of follow-up for each month xx time period takes the same definition above for the subject-years at-risk, however, follow-up does not stop at the time of first event.
 
- Additionally, for some exposure strategies (e.g. 'As-Exposed' strategy), time to treatment switch and risk windows are also considered when categorizing follow-up time into exposed and unexposed period (Section 9.2.1.2)
 
- All events experienced during the follow-up period including recurrent events are counted (see Section 9.2.1 for time period considered for each exposure strategy).
 



- Calculation of an individual's subject-years of follow-up for each exposure strategy is shown in Appendix 2 (Section 9.2).

 
Incidence and event rates will be calculated and reported per 100 subject-years. The 95% CI for the rate will be calculated assuming an exact Poisson distribution method [Stokes, 2012].

Model Checking & Diagnostics

• No model-based statistical analysis will be performed; hence there is no model checking and diagnostics to be conducted.

Results Presentation
Total number of events, number and % of subjects with events, total subject-years at-risk, and total subject-years of follow-up will be reported. In addition, incidence proportion (where applicable), incidence rate, event rate and their 95% CI will be presented. The mock-shell tables showing details of data displays are presented in Appendix 12.
Subgroup Analyses
This analysis may be conducted for each study cohort separately (Current Users and Treatment Initiators; Section 5.6.2) . The list of TLF Data Displays is presented in Appendix 11.
Sensitivity Analyses
This analysis will also be conducted using the 'Evaluable Sensitivity' population. Details of the planned displays are provided in Appendix 11: List of TLF Data Displays.

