Infections are responsible for morbidity and mortality in 25-50% of SLE patients; they are the primary cause of death in SLE patients in developing countries (Alarcón et al, 2001; Cervera et al, 1999 and Alarcón, 2006) In a multi-center European study in which 1,000 SLE patients were followed for more than 5 years, infections and disease activity were found to be responsible for more than half of all deaths. Moreover, patients with SLE have higher rates of infections and poorer outcomes compared to the general population (Doria et al, 2008; Petri, 1998). The microorganisms responsible for the overwhelming majority of infections in patients with SLE are bacteria. However, there are many reports of infections occurring in patients with SLE with various outcomes as a consequence of other microorganisms. The increased susceptibility to infections may be multifactorial. Disease activity has been shown to be an independent risk factor for the occurrence of infections (Petri et al, 1992; Zonana-Nacach et al, 2001) presumably because of the abnormal cellular function and complement abnormalities that are more pronounced in the affected patients. The use of corticosteroids and other immunosuppressive medications has also been associated with the increased occurrence of infections in SLE (Gladman et al, 2002; Noel et al, 2001 and Petri et al, 1992). Consequently, the possibility exists that an increased occurrence of infections may occur as a consequence of cytokine suppression, resulting in multiple cellular functional abnormalities (Boumpas et al, 1993).

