8.2 Sample Size Consideration

This registry will enroll approximately 3,000 patients approximately 2,000 receiving or initiating BENLYSTA plus standard of care (BENLYSTA cohort) and 1,000 standard of care only (comparison cohort). Each patient will be followed for 5 years, contributing a total of approximately 7,773 patient years in the BENLYSTA cohort and 3,886 patient years in the

comparison cohort, respectively, assuming a 10% annual patient drop-out rate and not accounting for crossover.

The registry will allow the difference in mortality rate in the BENLYSTA cohort and comparison cohort to be established with a 95% CI of +/-0.30 per 100-subject years, based on an estimated mortality rate of 0.68 per 100-subject years in both treatment groups (Table 8-1). The estimated mortality rate was based on the mortality rate in the pooled IV primary safety database in SLE subjects derived from 3 randomized, double-blind, IV placebo-controlled trials, referred to as IV SLE CRD studies (ie, integrated database of LBSL02 [placebo-controlled treatment phase only], HGS1006-C1056, and HGS1006-C1057) for all subjects (IV belimumab and placebo) adjusted for subject years. The precision of the rates of the AESI are provided in the table below:

Table 8-1 Precision of differences in AE rates estimated from a total of 7773 patient years in the BENLYSTA cohort and 3886 patient years in the comparison cohort, respectively

Adverse Events	Reference Rate¹ (per 100-patient years)	95% Confidence Interval for difference in AE rates² (per 100-patient years)
All Deaths	0.68	±0.32
Serious infection	5.80	±0.93
Opportunistic infection	0.136	±0.14
Malignancy excl. NMSC	0.226	±0.19
NMSC	0.226	±0.19
Serious Psychiatric Events	0.410	±0.25

¹ The reference AE rates were based on the AE rates in the pooled IV primary safety database derived from 3 IV SLE CRD studies (LBSL02, HGS1006-C1056, HGS1006-C1057) and adjusted for subject years.

² Assuming that the AE rates in BENLYSTA and the control groups were the same as the reference rate.

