**7.1.5.2. Statistical Methodology Specification related to study withdrawal event**

Endpoint / Variables

 
• Study Withdrawal event
 

Endpoint Specification

1. The percentage of subjects withdrawing from the study at the time of the final analysis data cut will be calculated for each exposure group, using the Kaplan-Meier product-limit estimator for the survival probability (the probability of not withdrawing from the study), as follows:
 $\hat{S}(t) = \prod_{t_i \leq t} \left(1 - \frac{d_i}{n_i}\right)$ 
 
- <math>t_i</math> is the specific time of interest when at least one event occurred
 
- <math>d_i</math> is the number of dropout events at time <math>t_i</math>.
 
- <math>n_i</math> is the number of subjects at-risk up to time <math>t_i</math>.
 
 
2. Withdrawal rates at time <math>t</math> will be computed at time <math>t</math>, denoted as <math>\hat{F}(t)</math>:
 $\hat{F}(t) = 1 - \hat{S}(t)$ 
The probabilities of survival and study withdrawal will be expressed in percentage (%), along with 95% CI, for the following time points: 12, 24, 36, 48, 60 months. Additionally the cumulative number of withdrawals will be presented, along with percentage (calculated as cumulative number of withdrawals/N).
 
For the following time periods: 0-12, 12-24, 24-36, 36-48, 48-60 months, the number at-risk at the start of each time period, along with number of withdrawals during each time period will be presented. Percentage is calculated as <number of withdrawals during time point> / <the number at risk at the start of time period>

Model Checking & Diagnostics

 
• No model-based statistical analysis will be performed; hence there is no model checking and diagnostics to be conducted.
 

Results Presentation

The mock-shell tables showing details of data displays are presented in Appendix 12.

Subgroup Analyses

This analysis may be conducted overall and for each study cohort separately (Current Users and Treatment Initiators; Section 5.6.2) and by relevant clinical covariate listed in Section 5.6.1. The list of TLF Data Displays is presented in Appendix 11.

Sensitivity Analyses

N/A

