## NOTE:

- i. Individual's subject-years at-risk will be calculated for each event type separately and if required for each time period (i.e. for analysis by time period)
- ii. Individual subject-years of follow-up may be required for each time period (i.e. for analysis by time period)

\* Last Contact Date as defined in section 9.5.3

2. While On Initial Exposure analysis approach will be used to analyze all data accrued up to the first treatment switch. Any events and follow-up time accrued after the first exposure switching (switching from Initial Exposure) will be censored (i.e. excluded from analysis) at first exposure switch date (see Section 5.14 for the definition of exposure/medication switching).

A limitation of this analysis approach is potential bias introduced by underreporting of events experienced during the study since data from only a subset of the study period and events collected before the first treatment switch are included in the analysis. The results only present risk of exposure prior to first treatment switch. See Section 9.2.1.2 for details of 'As-Exposed' (Time Varying) approach to address this.

**Programming Hints for derivation of essential variables needed for computation of incidence and events rates (presented in Section 7.1.5.1) under the While On Initial Exposure approach:**

- Compute First Switch Date as:  

$$\text{Baseline Benlysta Medication End Date} + 98 \text{ days (for switching from Benlysta to Non-Benlysta) or}$$

$$\text{First Post-Baseline Benlysta Start Date} - 1 \text{ (for switching from Non-Benlysta to Benlysta)}$$
- Compute individual's subject-years at-risk as:  

$$[(\text{minimum (Event Date, First Switch Date, Last Contact Date}^*) - \text{Study Enrollment Date}) + 1] / 365.25$$

- Compute individual's subject-years of follow-up as:
 
$$\frac{[(\text{minimum}(\text{First Switch Date}, \text{Last Contact Date}^*) - \text{Study Enrollment Date}) + 1]}{365.25}$$
- Consider events experienced up to First Switch Date (if switching from Initial Exposure) or whole study period (if no switch):
 
$$\text{Study Enrollment Date} \leq \text{Event Date} \leq \text{minimum}(\text{First Switch date}-1, \text{Last Contact Date}^*)$$
  - For incidence rate calculation only count new cases (i.e. first onset) of the event experienced during the period
  - For events rate calculation count all the events experienced during the period

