### 9.2.1.2. As-Exposed (Time Varying)

This exposure strategy specifically accounts for treatment switching to or from BENLYSTA throughout the study. It dynamically assigns subjects' exposure group based on Benlysta/non-Benlysta use at time of event, during study follow-up. Therefore, a subject's exposure group can change over time (time varying) depending on the SLE medication in use at specific time during study follow-up. For Benlysta, exposure does not end on the date when Benlysta stops. Instead, two different risk windows will be used to determine when Benlysta exposure ends:

- 14 weeks: Benlysta exposure ends 14 weeks (98 days) after Benlysta treatment stops.
- 6 months: Benlysta exposure ends 6 months (183 days) after Benlysta treatment stops.
- Subjects may contribute events and follow-up time (i.e. subject-years) to either one or both exposure periods depending on the medication switch pattern (see Section 9.2.2). Data summary and analysis will be done by exposure group assigned using the 'As--Exposed' strategy.

In contrast to the 'Initial Exposure' or 'While on Initial Exposure' strategies, which may only utilize subject level exposure group at Enrollment, the 'As-Exposed' strategy (time-varying) will assign and use exposure group at the time of the event.

**Programming Hints for derivation of essential variables needed for computation of incidence and events rates (presented in Section 7.1.5.1) under the 'As-Exposed' approach:**

- Each subject's follow-up time will be split into different exposure periods categorized as 'Exposed' (when the subject is on Benlysta medication) or 'Unexposed' (when the subject is off Benlysta). Each exposure period will have a distinct '*Period Start Date*' and a distinct '*Period end date*'.
  - Note that for each subject, number of exposure periods = number of switches + 1 (see Section 5.1 4 for definition of switching)
- Identify the start of each period as follows:
  - The first exposure period (i.e. period=1) starts from enrollment date (i.e. ***Period Start Date*** = Enrollment Date). First period exposure status is same as baseline exposure group assignment
  - For subsequent exposure periods, ***Periodn+1 Start Date*** is ***Periodn End Date*** + 1
- Identify the end of each period as follows:
  - For all exposure periods except the last, ***Period End Date*** = ***Switch Date***  
***Switch Date*** is  

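### The While On Initial Exposure, As-Exposed and Ever-Exposed rates carry no follow-up-time term, so a shared trend in risk can look like a group difference when switching spreads the groups' person-time unequally over follow-up

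*SAP*

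**What the plan says.** SAP 7.1.5.1 defines the incidence rate and the event rate as counts over subject-years per exposure group, with an exact Poisson interval for each group and no model. On time periods it states that "the follow-up time included in the subject-years at-risk calculation, for each month xx time period, starts from enrollment date". SAP 9.2.1.2 applies the same rule at 12, 24, 36 and 48 months and overall, so each period contains the one before it.

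Two rules let switching shape the denominators:
- While On Initial Exposure (SAP 9.2.1.1): "Any events and follow-up time accrued after the first exposure switching (switching from Initial Exposure) will be censored".
- As-Exposed (SAP 9.2.1.2): "Subjects may contribute events and follow-up time (i.e. subject-years) to either one or both exposure periods depending on the medication switch pattern".

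Ever-Exposed (SAP 9.2.1.3) moves comparison patients to BENLYSTA for good once they start it.

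The weighted rates in SAP 7.3.1.5 are ratios of weighted totals. SAP 7.3.1 names a weighted Poisson regression, but the table in 7.3.3 lists no covariate adjustment, and no time term appears. By their titles, Tables 24.120 to 24.122 and 54.020 have no time split. SAP 5.1 makes the two Initial Exposure approaches primary and the other strategies exploratory. SAP 2.2 words the primary endpoint as a comparison of incidence rates between exposed and unexposed patients.

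**The concern.** A crude rate averages the event risk over whichever follow-up years a group happens to contribute. Two such averages are comparable if risk is flat over follow-up, or if both groups have the same spread of person-time. Switching can break the second condition. Under As-Exposed, patients who stop BENLYSTA give early years to BENLYSTA and later years to NON-BENLYSTA. Under While On Initial Exposure, the group that switches sooner keeps mainly early years.

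A shared trend is plausible, though the documents do not establish one. Entry requires active SLE (Protocol 5.1), and Protocol 1.1 says: "Disease activity has been shown to be an independent risk factor for the occurrence of infections". Infection risk could fall after enrollment. Ageing and accruing damage could push risk the other way. When more patients stop BENLYSTA than start it, a shared fall would read as harm on BENLYSTA and a shared rise as protection.

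Propensity weights fixed at enrollment cannot remove this, because the imbalance arises later and would arise even if switching were random. It matters because the SAP presents As-Exposed as the answer to the stated limitations of ITT and of While On Initial Exposure, and neither statement mentions follow-up time.

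**Working it through.** **The plan's own figures.** Protocol 8.2 says "Each patient will be followed for 5 years, contributing a total of approximately 7,773 patient years in the BENLYSTA cohort" and 3,886 in the comparison cohort, "assuming a 10% annual patient drop-out rate and not accounting for crossover". With a constant drop-out hazard, patient-years = n × (1 − 0.9^5) / (−ln 0.9). This gives 7,773.5 for n = 2,000 and 3,886.8 for n = 1,000. The half-width for serious infection at 5.80 per 100 patient-years is 1.96 × √[0.058 × (1/7,773 + 1/3,886)] = 0.927 per 100, against the stated 0.93. Both reproduce.

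**Model with no drug effect.** Let λ(t) be the risk at follow-up time t, the same in both groups, and w_j(t) the person-time of group j at t. The crude rate is then ∫λ(t)w_j(t)dt / ∫w_j(t)dt. The two rates agree if λ is constant or if w_1 and w_2 have the same shape.

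**Inputs.** From the documents: 2,000 and 1,000 patients, 5 years, 10% annual drop-out, 5.80 per 100 patient-years, and 98 days of carry-over after stopping. Assumed, because the documents give neither: one switch per patient at a constant rate, and a log-linear change in λ over 5 years, scaled so that the ITT rate is 5.80.

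**Results** (BENLYSTA vs NON-BENLYSTA per 100 patient-years; true ratio 1.00):

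| Risk over 5 years | Stop / start per year | As-Exposed | While On Initial Exposure |
|---|---|---|---|
| halves | 30% / 5% | 6.16 vs 5.53, ratio 1.11 | 6.25 vs 5.88, ratio 1.06 |
| halves | 10% / 10% | ratio 1.03 | ratio 1.00 |
| halves | 10% / 30% | 5.80 vs 5.79, ratio 1.00 | 5.96 vs 6.26, ratio 0.95 |
| doubles | 30% / 5% | 5.44 vs 6.07, ratio 0.90 | 5.35 vs 5.72, ratio 0.94 |
| falls to one third | 30% / 5% | 6.37 vs 5.37, ratio 1.19 | ratio 1.10 |
| any trend | none | ratio 1.00 | ratio 1.00 |

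The ITT ratio is 1.00 throughout, given equal drop-out.

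**Hand check of the first row.** The mean follow-up time of As-Exposed person-time is 1.83 years (exposed) and 2.62 years (unexposed), a gap of 0.79. Halving over 5 years is a log slope of ln 2 / 5 = 0.139 per year. Then exp(0.139 × 0.79) ≈ 1.12, close to 1.11.

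**Do the cumulative tables help?** In the first row, the As-Exposed ratios at 12, 24, 36, 48 and 60 months are 1.01, 1.03, 1.05, 1.08 and 1.11. Within separate years they are 1.00 to 1.01. Cumulative windows show the drift but do not remove it. Separate years do.

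**Sensitivity to the model.** If risk changes in yearly steps from year 1 to year 5, the effect is somewhat larger. With risk halving, the As-Exposed ratio is about 1.10 at 20% stopping and 5% starting, and about 1.14 at 30% and 5%. While On Initial Exposure is about 1.04 and up to 1.08. Ever-Exposed, with risk halving and 10% a year of comparison patients starting, gives 5.84 vs 6.10, ratio 0.96. If stoppers restart BENLYSTA at 20% a year, the As-Exposed ratio at 20% stopping drops from about 1.10 to 1.06.

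**Against random error.** In the first row the As-Exposed shift is 6.16 − 5.53 = 0.63, against a half-width of 0.88. Only the fall to one third exceeds it (1.00 against 0.88). An 11% shift for deaths is 0.11 × 0.68 = 0.07 against the stated ±0.32. For opportunistic infection it is 0.11 × 0.136 = 0.015 against ±0.14.

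**The case against.** The strongest reply is that the plan is descriptive. SAP 2.4 and 5.7 rule out formal testing, and the only AESI intervals specified are one per group. A reader might simulate this and infer an inflated false-positive rate. One such run (risk halving, 20% stopping) had the interval for the As-Exposed difference excluding zero in 22% of trials instead of 5%. That figure belongs to a rate-difference interval that the SAP does not plan, and to the commonest event, so it should not be used against the plan. The shift in the ratio remains, because SAP 2.2 still asks for the rates to be compared.

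A reader might also infer that any shared trend is always charged to one group. The documents do not support that. Bias needs both a trend and unequal spread of person-time, and the table shows ratios of 1.00 where either strategy happens to be balanced. Protocol 8.1 expects some patients to restart BENLYSTA, which weakens the effect. No falling trend is documented: Protocol 5.1 sets no activity threshold, and current users are enrolled, so entry need not coincide with a flare.

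The largest shifts are in exploratory tables. ITT, the other primary approach, is unaffected under equal drop-out. All of this stands.

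The last reply is that yearly rates could be obtained by subtracting cumulative totals. That may work for some tables, but the plan does not ask for it, the overall and weighted tables have no split to subtract, and the mock shells are in a separate file and cannot be checked.

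**Conclusion.** The point holds in a limited form. The rates under While On Initial Exposure, As-Exposed and Ever-Exposed are crude or cumulative from enrollment, and nothing in the plan separates drug exposure from time since enrollment. A shared trend therefore biases these comparisons whenever switching gives the groups different follow-up-time distributions.

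With risk halving or doubling over 5 years, the null ratio for serious infection is about 0.90 to 1.14 for As-Exposed and 0.94 to 1.08 for While On Initial Exposure. It is nearer 1 when patients restart BENLYSTA; similar switching rates in the two groups also bring it nearer 1. These ranges rest on assumed switching and an assumed trend. They illustrate the size and are not bounds. The shift usually stays inside the half-width, and for the rarer AESIs it is minor beside random error. This is a worthwhile, inexpensive improvement to the plan. It does not show that the primary results will mislead.

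**What to change.** In SAP 7.1.5.1 and 7.3.1.5, for these three strategies where each is planned:

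- Tabulate events and subject-years by group in separate follow-up years. SAP 7.1.5.2 already does this for withdrawal: "For the following time periods: 0-12, 12-24, 24-36, 36-48, 48-60 months".
- Beside the crude rates, report a comparison adjusted for follow-up year. Either standardise each group's rate directly to the pooled subject-year distribution, or fit a Poisson model with follow-up year as a class term. These are alternatives that estimate different summaries, so name one in advance.
- For the weighted While On Initial Exposure table, use a robust (sandwich) or bootstrap variance. Weighted counts in the Poisson formula ignore the variability of the weights.
- For rare AESIs, merge years. Where a stratum is empty, show the crude rates with the separate-interval counts only. Opportunistic infection expects about 0.136 × 38.86 ≈ 5 comparison-cohort events in total.
- State that any group difference in these tables is to be read together with the time-adjusted result.

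The cost is SAP wording and one further split of person-time that already has period start and end dates. The price is slightly wider intervals and merged years for sparse AESIs.
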